14	FUNDING AND SUPPORT	50
14.1	Financing	50
15	INSURANCE	51
16	REFERENCES	52
17	APPENDIX	53

SUPSI

Study Synopsis

Sponsor / Sponsor-Investigator	Sponsor Thim van der Laan AG [name] [name] Investigator University of Applied Sciences Department of Business Economics, Health and Social Care Physiotherapy Graubünden Attn: [name] [name]
Study Title:	Local changes in skin characteristics during and after a topical application of a warming or cooling product - a randomized, controlled, clinical trial.
Short Title / Study ID:	Local changes in skin characteristics during and after a topical application of a warming or cooling product
Protocol Version and Date:	Version 04 from 24.06.2019
Trial registration:	Cantonal Ethics Committee Zurich
Study category and Rationale	Observational study of category A according to KlinV (Art. 20)
Clinical Phase:	-
Background and Rationale:	
In the field of sports medicine and physiotherapy, but also on a private basis, warming or cooling topical products are used. The indications include acute and chronic complaints of the musculoskeletal system¹. Widely used and frequently described in the literature, topical products containing diclofenac as a nonsteroidal anti-inflammatory drug (NSAID) for pain relief^{2,3}. The application forms vary from gels to patches. However, the evidence of effectiveness is low^{2,4,5,6,7}. Lasanen et al. came to a similar conclusion in 2015, who were unable to observe any significant effect of menthol concentration on skin cooling⁸.
 
A large number of these over-the-counter products are presented and advertised in daily advertising on television (including Flexor Tissugel, Voltaren Emulgel, Perskindol Cool Patch-N.).

SUPSI

Objective(s):	The aim of this study is to investigate the local changes in skin characteristics during and after warming or cooling topical product applications without drug additives such as diclofenac, ibuprofen, etc. using non-invasive methods. The area of application includes the lumbar back.
Outcome(s):	
Primary results in the application area during application and over the course of up to one hour of post-application in 10-minute intervals (time 0min, 10min, 20min, 30min, 40min, 50min, 60min):
 
 - Perfusion of skin microcirculation (Laser Speckle Contrast Imager, High Power Laser Doppler), (ultrasound X-flow (baseline only and 60min post-application)) - Erythema formation (chromameter) 
 o of the skin o of the superficial muscles - Surface skin temperature (i-button, infrared thermometer, thermal imaging camera) 
 o of the skin - Oxygen Saturation (Near-Infrared Spectroscopy) 
 o of the superficial muscles - Subjective parameters 
 o Perceived temperature (-4 very cold to +4 very hot) o Thermal comfort (0 pleasant to 4 extremely uncomfortable) 
Secondary results within a 5cm radius of the application area during application and in the course of up to one hour of post-application in 10-minute intervals (time 0min, 10min, 20min, 30min, 40min, 50min, 60min):
 
 - Perfusion of skin microcirculation (Laser Speckle Contrast Imager, Ultrasound X-flow, High Power Laser Doppler) - Erythema formation (chromameter) 
 o of the skin o of the superficial muscles - Surface skin temperature (i-button, infrared thermometer, thermal imaging camera) 
 o of the skin - Oxygen Saturation (Near-Infrared Spectroscopy) 
 o of the superficial muscles - Subjective parameters 
 o Perceived temperature (-4 very cold to +4 very hot) o Thermal comfort (0 pleasant to 4 extremely uncomfortable)
Study design:	Randomized, controlled, clinical trial

SUPSI


Inclusion / Exclusion criteria:
	
Margin criteria:
 
 - Adults aged 18 to 40 years - No surgical interventions on the musculoskeletal apparatus in the area of the trunk (neck C7 to pelvis, sacrum and hip joints) - Injuries to the trunk that occurred more than a year ago and do not cause any symptoms (pain at rest or during exertion, swelling, redness, restriction of movement of the adjacent joints) - Closed skin and scar conditions 
Exclusion criteria:
 
 - Age over 40 years - Surgical interventions on the musculoskeletal apparatus in the area of the trunk (neck C7 to pelvis, sacrum and hip joints) - Current injuries of any kind (skin abrasions, burns, sprains, muscle or tendon strains, bruises, fractures) in the area of the trunk that are still symptomatic - Scars in the lumbar back area - Fear of application - Regular intake of medication (including self-purchased medication), with the exception of contraception drugs - Metal implants in the torso area - Known allergy to a possible ingredient of the products (wintergreen oil, menthol, alcohol) - Lack of epicritical and protopathic skin discrimination in the lumbar dorsal area (Th10-L5) (pointed-blunt, warm-cold, sense of vibration at the lateral malleoli) - Renal failure - Bronchial asthma - Pregnancy / breastfeeding - Diabetes mellitus type 1 or 2 - Polyneuropathies
---	---

SUPSI

Preparation	
Subject recruitment
 
The subject information and declaration of consent are submitted. Questions may be asked. If the subject agrees with the information, he or she will be summoned to the first day of contact. This includes the explanations on site, the signature of the declaration of consent, the completion of the health questionnaire and the screening test. This includes a skin discrimination test both epicritically and protopathically (warm-cold, pointed-blunt, sense of vibration) of the lumbar back area paravertebral on both sides. If the test is passed, a possible skin intolerance to the products to be applied is ruled out. For this purpose, a small product sample is applied to the volar forearm and the reaction is waited for during 10 minutes of post-application. If excessive redness and/or itching, pain, uticalia occurs, the subject will be excluded from the study. The pregnancy test must be negative (women only). If all tests are passed, an appointment is made for the intervention. The subject must follow the following rules: do not apply body lotion to the back, do not consume any meal or drinks (coffee / tea / alcohol – water allowed) 2 hours before the appointment⁹.
 
Test Subject Preparation Measurement Day
 
The test subject lies topless in a prone position on a treatment table, women in bras. First, the lumbar back area is rubbed on both sides with distilled water (room temperature) and a soft cotton cloth with light pressure. This is followed by the 20-minute room acclimatization phase in the same storage¹⁰. The room temperature is kept as constant as possible (deviation of $\pm 2^{\circ}\text{C}$), the window blinds and windows are closed, and the ceiling lighting is minimal.

--------------------	---

SUPSI


Measurements and procedures:
	
After the 20-minute acclimatization phase, the application area is drawn (skin-friendly pen), the template (recess 10cm x 10cm) is applied and the baseline measurements (a-e) are performed. After the baseline measurement, the product is applied (3g)⁸. The product is applied until it can no longer be distributed. The research employee wears a glove. This is followed by the measurements (a-d) at 0min, 10min, 20min, 30min, 40min, 50min, 60min post-application.
 
a) Perfusion of skin microcirculation
 
The perfusion of the skin microcirculation is performed using the Laser Speckle Contrast Imager (moorFLPI 2, moor instruments, www.moor.co.uk), the High Power Laser Doppler (moorVMS-LDF1-HP, moor instruments, www.moor.co.uk) and the ultrasound X-Flow (esaote MyLabClassicC, Maastricht, Netherlands, www.esaote.com). Since the contact gel, which is required for the ultrasound X-Flow measurement, could interfere with the product application, or could interfere with the subjective temperature perception of the subject, the ultrasound measurement is only measured at the time of baseline and 60min post-application. This was after questioning the subjective parameters.
 
b) Erythema formation
 
Erythema formation is visualized using the chromameter (www.konicaminolta.eu). The chromameter measures the light reflection and absorption of the skin.
 
c) Skin surface temperature
 
The surface temperature of the skin is measured using an infrared thermometer (Votcraft InfraRed Thermometer, IR 800-20D) and the i-buttons. The iButton system consists of self-adhesive sensors that wirelessly transmit skin temperature information to a computer (www.ibuttonlink.com). In addition, a thermal imaging camera (www.csem.ch) records the skin surface temperature.
 
d) Oxygen saturation of the superficial muscles
 
The oxygen saturation of the superficial muscles is determined using the near-infrared measurement method (moorVMS-NIRS, moor instruments, www.moor.co.uk) The measurement is non-invasive and painless. The sensors are placed on the corresponding muscles.
 
e) Subjective Perception Parameters
 
The test subjects indicate their subjective temperature perception on a scale of 9 points from -4 (very cold) to +4 (very hot). They then rate the thermal comfort on a 5-point scale between 0 (pleasant) and 4 (extremely unpleasant)¹¹.
 
Further processing of the data
 
Windows uses Excel for data pooling and the graphical representation of the end data®.

--	---

SUPSI

Study Product / Intervention:	Over-the-counter, topical ointments/creams/gels with a warming or cooling effect
Control Intervention (if applicable):	The mutual paravertebral area of the lumbar back, which does not receive any application, acts as a control.
Number of Participants with Rationale:	
We limit the number of subjects to N = 45 per warming or cooling product. A total of N = 90 subjects will be recruited.
 
As part of a planned sub-analysis, an additional N = 15 subjects will be recruited. Thus, the total number of subjects increases to N = 105.
 
Previous studies on topical diclofenac applications have tested groups of up to 200 subjects^{4,6,7}. Roth et al. 2004 limited themselves to N = 80 subjects¹². Lasanen et al. 2016 tested N = 10 subjects, they used a gel without drug ingredients⁸.

Study Duration:	March 2017-December 2020
Study Schedule:	
March 2017: effective start of measurements
 
December 2020: planned end of measurements

Investigator(s):	
Examiner
 
 - [name]^{1,2} - [name]^{1,2} - [name], Drs, MSc^{1,2} - [name], MSc² 
<small>1University College Physiotherapy "Thim van der Laan", [name] 2University of Applied Sciences and Arts Southern Switzerland, Department of Business Economics, Health and Social Care, Physiotherapy Graubünden, [name]</small>
 
Contact / Director of Studies [name], PhD University of Applied Sciences and Arts Southern Switzerland Department of Business Economics, Health and Social Care Physiotherapy Graubünden [name] [contact] [contact]

SUPSI

Study Centre(s):	
Single Centre Study:
 
University of Applied Sciences and Arts Southern Switzerland Physiotherapy Graubünden [name]

Statistical Considerations:	
Local changes in skin characteristics during and after a topical application of a warming or cooling product - a randomized, controlled, clinical trial.
 
Repeated measures analysis of variance (MANOVA)
 
2 factors:
 
 - Topical application (warming versus control / cooling versus control) - Time (baseline, time 0min, 10min, 20min, 30min, 40min, 50min, 60min post-application) 
The significance level is set at $P < 0.05$, and the statistical data analysis is carried out with SPSS V. 23.

GCP Statement:	
This study will be conducted in compliance with the protocol presented here, the current version of the Declaration of Helsinki, the ICH-GCP, ISO EN 14155 (where applicable), and the Swiss Human Research Ordinance HFV.

SUPSI

Overview of the study

The use and application of topical products for local pain relief in chronic or acute musculoskeletal apparatus complaints are widespread. Advertising propagates corresponding products from various pharmaceutical manufacturers with pain-relieving and circulation-promoting long-term effects. The products used in this study (ointments, creams, gels) are all commercially available without a prescription. Science is extensively concerned with the field of application and effectiveness of topical NSAID products on chronic pain in osteoarthritis^{2,3}. Topical products have the advantage over oral medications of bypassing the gastrointestinal tract and thus avoiding possible side effects¹. The application forms vary from sprays to gels to plasters. Derry et al. 2016 describe in their review that topical NSAID products achieve significant pain relief in subjects with osteoarthritis compared to placebo treatment². The authors found no significance for other chronic pain conditions. Matthews et al. 2011 showed that topical applications with a hyperaemic effect (ingredient salicylate) were not successful in acute injuries and therefore recommended topical NSAID products for chronic pain conditions⁵. Several studies with different forms of application have been able to achieve pain relief through the use of topical NSAIDs^{4,6,12,13}.

Lasanen et al. 2016 tested different menthol concentrations of a cooling gel for skin cooling and concluded that all tested concentrations cooled the skin up to an hour of post-application, but the effect appeared to be independent of the concentration. Furthermore, the surrounding skin area did not cool significantly⁸.

Aim of the study

The aim of our study is to investigate local changes in skin characteristics during and after a topical application of an over-the-counter, warming or cooling product without medicinal ingredients using non-invasive methods. Products with arnica or wallwort are excluded so as not to influence the subjective sensation of the subject. Products containing menthol, alcohol derivatives and wintergreen oil are included. The objective parameters are the perfusion of the microcirculation of the skin, erythema formation, skin surface temperature, oxygen saturation of the superficial muscles and the subjective temperature perception of the subject. The parameters are collected as a baseline before the application of the product, then directly in the postal application at 0 min, then in 10-minute intervals up to one hour of postal application. Thus, 8 measurement moments take place. The aim is to record the local changes in skin characteristics during and after a topical application and to recognize the effects of the products. The current state of scientific knowledge requires further studies with topical products without medicinal ingredients in order to substantiate or refute the effects already established.

Our preliminary study results of the effects of the warming products showed that one of the three tested products led to more significant changes in the measured skin parameters compared to the remaining two products. However, none of the three products had an effect on deeper tissue. However, this aspect is of great importance within rehabilitation and physiotherapy with regard to wound healing, regeneration and muscle tone. In the meantime, we have two more sensitive measuring instruments at our disposal, which can record the perfusion of the skin microcirculation up to the capillary bed and the oxygen saturation of the tissue up to a maximum depth of 30 mm. As part of a sub-analysis, we therefore plan to recruit additional N = 15 subjects to repeat the measurements with these more sensitive measuring instruments. The warming product with the greatest effect (shown above) serves as an intervention product.

Abbreviations

SUPSI

CEC	Competent Ethics Committee
GCP	Good Clinical Practice
Ho	Zero hypothesis
H1	Alternative hypothesis
KlinV	Ordinance on Clinical Trials in Human Research

SUPSI

Study Schedule

The completion of the measurement series is planned for October 2019, and the completion of the entire project for December 2020.

The sub-analysis is scheduled to be carried out from September to the end of October 2019. The data analysis will be carried out in November and December 2019. In 2020, the articles will be prepared and submitted for publication. The completion of the entire project (KEK, ZH ID 2016-01541) remains scheduled for the end of December 2020 as originally planned.

Table 1: Schedule

	January-February	March	April-June	July-October	November-December
2017		Subject information, screening, planning of measurements for warming products	Data collection	Data collection	Data collection
2018	Data processing	Data processing	Statistics	Statistics	Article Writing
2019	Subject information, screening, planning of measurements for cooling products	Data collection	Data collection	Data collection	Statistics
2020	Article Writing	Article Writing	Publication	Publication	Completion of the entire project

SUPSI

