The test subjects are comprehensively informed about the course of the study and possible risks before they are accepted to participate in the study. You will also receive the information in written form and have the opportunity to ask questions if anything is unclear. The declaration of consent explains to them what their rights and obligations are when participating. In addition, they are informed that they may withdraw from participation at any time without giving reasons, without incurring any disadvantages as a result. To clarify possible as yet unknown intolerances to an ingredient of the topical application, the product is tested on a small isolated skin area on the volar forearm, away from the actual application area to avoid interference. If there are positive signs of intolerance (including excessive redness, Local change in skin characteristics during and after a topical application of a warming or cooling product Version 04-24.06.2019

SUPSI

urticaria, itching, local swelling), the subject will be excluded from the study for safety reasons.

SUPSI

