8 STUDY INTERVENTION

8.1 Medical Device ID

8.1.1 Intervention product

The intervention products are topical ointments/creams/gels available without a prescription with a warming or cooling effect. The warming products are based on wintergreen oil, the cooling products on menthol and/or alcohol base. Eight different products are included. Of these, three products are said to have a warming effect (Axanova hot gel, Perskindol Dolo Gel, Dolor-X Hot Gel), three products to have a cooling effect and then a warming effect (Axanova activ gel, Perskindol Classic Gel, Dolor-X Classic Gel) and two products to have a cooling effect (Perskindol Cool Cooling Gel, Dolor-X Cool Gel).

In the context of the sub-analysis, the product Axanova hot gel serves as an intervention product.

Securing the test subjects

Only subjects who have completed the health questionnaire without risk factors, successfully passed the product testing without skin intolerance and the screening with regard to skin discrimination will be admitted to the study. In this way, at-risk test subjects are detected at an early stage and are not recruited for the study.

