9 STUDY STRUCTURE & EVALUATION

9.1 Schedule Study Protocol

1. **Contact by e-mail, then by phone by the director of studies**
 - a. Rough explanation of the study
 - b. Announcement of the inclusion and exclusion criteria, corresponding examination of the suitability of the test persons
 - c. If interested and suitable, delivery of further documents (see point 2)
2. **Subject information, declaration of consent**
 - a. Clarify possible questions
 - b. If the subject agrees, make an appointment for screening tests
3. **On-site explanations plus screening tests (pregnancy test (for women only), skin discrimination test, product skin compatibility), 1st day of contact**
 - a. Time required 30min
 - b. If the test person is suitable and consented, sign the declaration of consent and make an appointment for the actual measurement
4. **Measurement day on site, 2nd contact day**
 - a. 30min (cleansing of the skin in the application area and 20-minute room acclimatization, marking of the application area and adjustment of the measuring equipment)
 - b. Executing the test protocol (see Intervention)

Intervention

- Baseline measurement:	1min
- Application of topical product:	1min
- Follow-up measurement time 0min:	1min
- Follow-up measurement time 10min:	1min
- Follow-up measurement time 20min:	1min
- Follow-up measurement time 30min:	1min
- Follow-up measurement time 40min:	1min
- Follow-up measurement time 50min:	1min
- Follow-up measurement time 60min:	1min

Total Time Expenditure Intervention: approx. 100 min

The total time required for both contact days together results in a duration of 130 minutes per test subject.

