9.1.5 Collection of safety parameters

Apart from the health questionnaire (including pregnancy test for female subjects), the ability to discriminate against the skin and a skin compatibility test (product application in a small area on the volar forearm), no safety parameters are collected.

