9.2 Procedure at each visit of the test subjects

9.2.1 Single measurement

The project involves multiple visits. After contacting them by telephone and announcing the inclusion and exclusion criteria, the subject information and the declaration of consent are submitted for inspection and reading. If the subject agrees with the study conditions and criteria, he or she registers to make an appointment for the 1st contact day. The 1st contact day includes, in the order described, the; Explanations on site, signing the declaration of consent, filling out the health questionnaire, carrying out the screening tests (including pregnancy test for female subjects). If the subsequent screening tests have been passed, an appointment is made for the actual measurement day (2nd contact day).

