2.1 Preparation of the subject

The test subject lies with his upper body undressed for the men, women in a bra in a prone position on a treatment table. The lumbar back area is washed with distilled water (room temperature) and a soft cotton cloth to remove possible skin and fat residues. An alcohol solution is deliberately avoided so as not to influence the temperature perception of the test subjects. This is followed by a 20-minute room acclimatization to prepare the test subject for the measurements. The area of application (10cm x 10cm, paravertebral lumbar, randomized triggered) is drawn and the measuring apparatus is adjusted. This is followed by the baseline measurement.

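### The forearm intolerance test is read only for 10 minutes on contact day 1, and no written day-2 step re-checks it before 3 g goes on the back

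*Combined protocol and SAP*

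**What the plan says.** Known allergies are handled by the health questionnaire and the exclusion criteria. Unknown ones are the task of a product test, whose purpose 3.7 gives as follows: "To clarify possible as yet unknown intolerances to an ingredient of the topical application, the product is tested on a small isolated skin area". The synopsis (Preparation) sets the reading time: "a small product sample is applied to the volar forearm and the reaction is waited for during 10 minutes of post-application". Section 9.1 item 3 places the test on contact day 1.

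Admission depends on the result. Under 8.1.1, only participants who, among other conditions, "successfully passed the product testing without skin intolerance and the screening with regard to skin discrimination will be admitted to the study". Section 9.2.1 continues: "If the subsequent screening tests have been passed, an appointment is made for the actual measurement day (2nd contact day".

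For day 2, 9.1 item 4 gives the preparation as "30min (cleansing of the skin in the application area and 20-minute room acclimatization, marking of the application area and adjustment of the measuring equipment". Section 9.2.2 item 2.1 has the back washed, and then: "This is followed by a 20-minute room acclimatization to prepare the test subject for the measurements". Marking, equipment set-up, baseline, application of 3 g (item 2.2) and follow-up to 60 minutes (item 2.3) come next.

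Section 9.1.5 closes the list of safety checks. Beyond the questionnaire (with pregnancy test), the skin discrimination test and "a skin compatibility test (product application in a small area on the volar forearm), no safety parameters are collected".

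**The concern.** The forearm test is there to find people who should not receive the product. As written, its result is taken once, within 10 minutes of a small application. The participant then leaves and comes back for the larger exposure. If the forearm reacted in between, the day-2 procedure has no point at which this would come to light. Nobody is told to look or to ask, and 8.4 keeps conversation with participants to a minimum, so a spontaneous report cannot be relied on.

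The stake is participant safety. Participants are healthy volunteers with no direct benefit (3.7), so an avoidable exposure of someone who has already reacted has nothing to set against it. No estimate or test in the plan is affected: there is no safety analysis (11.4.5), and the primary comparison does not use the screening result.

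**Working it through.** The point is one of procedure, so the check is mainly a reading of the relevant sections side by side. Arithmetic enters only for the cost.

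**1. What happens at each stage**

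| Stage | Source | Forearm site looked at or asked about? |
|---|---|---|
| Day 1, product test | Synopsis Preparation; 3.7; 9.1 item 3 | Yes, for 10 minutes |
| Between the days | Interval not stated | No step written |
| Day 2, preparation | Synopsis Preparation; 9.1 item 4; 9.2.2 item 2.1 | No |
| Day 2, baseline and application of 3 g | Synopsis Measurements; 9.2.2 items 2.1 and 2.2 | No |
| Day 2, follow-up | 9.2.2 item 2.3 | No |
| Other safety parameters | 9.1.5 | None listed |

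**2. Is there a rule that would exclude a late reactor?** Yes. Section 3.7 excludes on positive signs of intolerance and ties this to no time window. A late reaction that somebody noticed would therefore already exclude. What is missing is detection.

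**3. Does the plan itself allow for reactions that a 10-minute reading may miss?**
- Section 4.4 accepts that intolerance reactions not recognizable at screening may occur.
- Section 10.3.1 lists eczematous lesions as rare and pronounced hypersensitivity as very rare.
- Section 6.3 has a rule for incidents more than 24 hours after application.

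None of these gives an onset time, so the share of reactions that start after 10 minutes cannot be computed.

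**4. Cost of a day-2 check**
- Length of day 2: 130 min in total - 30 min on day 1 = 100 min, which agrees with the figure of about 100 min in 9.1.
- Assumed duration of the check: 1 min. Share of day 2: 1/100 = 1%. If it took twice as long: 2/100 = 2%.
- Upper bound over the whole project: 105 x 1 min = 105 min = 1.75 h.
- Remaining participants: this protocol version is dated June 2019. The schedule puts data collection for the warming products in 2017, and the study overview reports preliminary results for them. If those 45 participants are complete, at most 105 - 45 = 60 remain, so at most 60 min at 1 min each, or 120 min at 2 min each.

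**The case against.** The strongest reply is that the harm is not shown. It needs a reaction that starts after 10 minutes and is still visible or remembered on day 2. The documents give no onset times and no interval between the days. That stands: no rate can be claimed, and a reaction that had faded and been forgotten would be missed even with the check.

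The safeguards around the exposure also stand. The single application is below the leaflet dosage (10.3.1). Known allergy, asthma and renal failure exclude. Water, wipes and cold packs are at hand (5.3), and an allergic reaction stops the experiment (9.1.5.1). The last two act only after the product is on the back, so they do not replace detection beforehand.

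A reader might infer three stronger things that the documents do not support:
- *That the synopsis promises certainty.* It says: "If the test is passed, a possible skin intolerance to the products to be applied is ruled out". In context the test passed is the skin discrimination test, and the sentence introduces the forearm sample as the next step. Section 4.4 openly accepts residual risk.
- *That a late reactor is formally cleared for exposure.* Section 3.7 has no 10-minute limit, so a late reaction that is noticed falls under the existing exclusion.
- *That the forearm is certainly never re-checked.* The data sheet in Appendix item 3 covers both screening and measurement and is not supplied. A check may be recorded there. The gap shown is in the protocol text.

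**Conclusion.** The point holds as a minor participant-safety gap. The test for unknown intolerance is read once, for 10 minutes on day 1, and no written day-2 step would detect a later reaction before 3 g is applied to 100 cm2 (10 cm x 10 cm) of the back. The rule to exclude such a person is already in 3.7; the step that would bring it into play is absent.

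The number of participants affected is unknown and probably small. This rests on the frequency words in 10.3.1 and not on any rate. The conclusion assumes that the unsupplied sheet contains no day-2 check; if it does, the protocol only needs to say so. No planned analysis or result changes.

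**What to change.** In 9.1 item 4 and 9.2.2 item 2.1, add one sentence each. Before any product is applied on day 2:
- inspect the forearm test site;
- ask whether any reaction has occurred since day 1;
- record the finding on the existing screening and measurement sheet;
- exclude the participant if a sign that already excludes at screening is seen or reported (excessive redness, itching, pain, urticaria or local swelling).

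The check fits within a visit that is already planned, needs no new criterion or equipment, and leaves the measured area on the back untouched. The cost is about one minute per remaining participant, one line on the sheet, and possibly a few more screening exclusions, which is the purpose of the check.
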